### **11.5.7       Contraception and Pregnancy**

#### **11.5.7.1     Contraception**

The effects of LUM monotherapy or LUM in combination with IVA on the PK of hormonal contraceptives are not known; however, since LUM is a strong inducer of CYP3A, it may reduce the effectiveness of hormonal contraceptives.

Participation in this study requires a commitment from the subject and his/her partner to use at least 1 effective method of birth control as a couple. Acceptable methods of contraception for participants of this study and their partners are listed below. Methods of contraception should be in successful use from at least 14 days before the first dose of LUM/IVA (unless otherwise noted) until 90 days following the last dose of LUM/IVA.

#### **Definition of Childbearing Potential**

All female subjects who have had their first menstrual period, from the time of the screening assessment through the Safety Follow-up Visit, including subjects with tubal ligations and subjects who do not have a documented hysterectomy, will be considered to be of childbearing potential unless:

- The subject has had a documented hysterectomy or bilateral oophorectomy/salpingo-oophorectomy
- The subject is postmenopausal, defined as at least 12 months of continuous spontaneous amenorrhea with serum FSH levels  $\geq 40$  mIU/L.

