**Table 3-1 Screening Period Assessments – Study VX15-809-114**

Assessment	Screening Period Day -28 to Day -1
Informed consent and assent (where applicable)	X
Inclusion and exclusion criteria review	X
Demographics	X
Height, weight, and BMI	X
Review of medical history (includes CFTR genotype) a	X
Ophthalmologic examination b	X
Prior and concomitant medications	X
Vital signs c	X
Physical examination d	X
Spirometry e	X
Serum pregnancy test (all female subjects of childbearing potential) f	X
Serum FSH g	X
Hematology h	X
Liver Function Testing i	X
AEs and SAEs	Continuous from signing of ICF or assent (where applicable) through Safety Follow-up Visit

AE: adverse event; BMI: body mass index; CF: cystic fibrosis; *CFTR*: *CF transmembrane conductance regulator* gene; FSH: follicle-stimulating hormone; ICF: informed consent form; IVA: ivacaftor; LUM: lumacaftor; PE: physical examination; SAE: serious adverse event; [REDACTED]

a Genotype testing will be performed if this is not documented in medical history. CF genotyping can be waived with documented *CFTR* genotype ([Section 11.5.2](#)).

b An ophthalmologic examination will be conducted by either a licensed ophthalmologist or an optometrist for all subjects <18 years of age. The exam may be waived if there is documentation of an exam within 3 months of the date of informed consent (or assent, when applicable). Subjects with documentation of bilateral lens removal do not need the ophthalmologic examination ([Section 11.5.6](#)).

c Vital signs will be assessed following a 5-minute rest in the seated or supine position.

d Physical examination of all body systems ([Section 11.5.4](#)).

e Spirometry may be performed pre- or postbronchodilator ([Section 11.5.5](#)).

f Any female subject initiating LUM/IVA combination therapy who is considered to be of childbearing potential should have a serum pregnancy test. Women of childbearing potential are defined as: female subjects after puberty unless they are postmenopausal for at least 1 year and have documented FSH levels within the postmenopausal reference range of the performing laboratory, or are surgically sterile.

g Serum FSH levels will be measured for any suspected postmenopausal female subjects with at least 12 months of continuous spontaneous amenorrhea.

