**Table 3-2 Treatment Period and Safety Follow-up Visit Assessments – Study VX15-809-114**

Event/Assessment	Day 1	Week 12	Week 24	Week 36	Week 48	Safety Follow-up Week 52 a
Clinic visit	X	X	X	X	X	X
Vital signs b	X	X	X	X	X	X
Physical examination c					X	X d
Liver Function Testing e	X	X	X	X	X	X
Urine pregnancy test (all female subjects of childbearing potential)	X	X	X	X	X	X
Randomization f	X					
Standardized education on adherence	X					
Concomitant medications, treatments, and procedures	X	X	X	X	X	X
Smart Adherence Technology-Reported Adherence g		X	X	X	X	

LUM/IVA drug count i		X	X	X	X	
Ophthalmologic examination j					X	
AEs and SAEs	Continuous from signing of ICF or assent (where applicable)					
LUM/IVA resupply	Every 3 months throughout study					

AE: adverse event; ICF: informed consent form; IVA: ivacaftor; IWRS: interactive web response system; LUM: lumacaftor; PE: physical examination; SAE: serious adverse event; [REDACTED]

a The Safety Follow-up Visit is 28 ( $\pm$  7) days after the last dose of LUM/IVA (Section 8.1.3).

b Vital signs will be assessed following a 5-minute rest in the seated or supine position.

c Symptom-targeted PEs will occur at any time during the study if triggered by AEs or if deemed necessary by the investigator.

d Required for subjects who do not begin commercial LUM/IVA after Week 48 only.

e Day 1 only blood draws will be collected before the first dose of LUM/IVA. Liver function testing (alanine aminotransferase [ALT], aspartate aminotransferase [AST], gamma-glutamyl transpeptidase [GGT], alkaline phosphatase [ALP], and total bilirubin) must be performed at the scheduled visits (Section 11.5.2).

f Randomization must occur after all inclusion and exclusion criteria are met and before the first dose of LUM/IVA. Randomization will be done through IWRS.

g Data will be collected for all subjects throughout the study in real-time. Subjects in Study Arm A will review data with physicians at study visits.

i LUM/IVA drug count will be collected at the end of specified study visits.

j See Section 11.5.6.

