### 8.1.3 Follow-up

Subjects will have a Safety Follow-up Visit 28 ( $\pm$  7) days after the last dose of LUM/IVA. Safety Follow-up Visit assessments are listed in [Table 3-2](#). Subjects who begin commercial LUM/IVA before this visit do not have to complete the Safety Follow-up Visit.

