## 9.2 Exclusion Criteria

Subjects who meet any of the following exclusion criteria will **not** be eligible.

1. History of any illness or any clinical condition that, in the opinion of the investigator, might confound the results of the study or pose an additional risk in administering LUM/IVA to the subject, e.g., history of advanced liver disease.
2. Presence of moderate or severe hepatic impairment (Child-Pugh Class B or C).
3. Subjects currently receiving invasive mechanical ventilation.
4. Known history of alcohol or drug abuse in the past year, including but not limited to cannabis, cocaine, and opiates, as deemed by the investigator.
5. Any of the following abnormal laboratory values during screening:
  - o Alanine aminotransferase (ALT) or aspartate aminotransferase (AST)  $>5 \times \text{ULN}$
  - o ALT or AST  $>3 \times \text{ULN}$  with total bilirubin  $>2 \times \text{ULN}$
  - o Glomerular filtration rate  $\leq 30 \text{ mL/min/1.73 m}^2$ . This will be calculated by the Modification of Diet in Renal Disease study equation for subjects  $\geq 18$  years of age and calculated by the Counahan-Barratt equation for subjects aged 12 to 17 years.
6. Pregnant or nursing females (females of childbearing potential must have a negative pregnancy test at screening and Day 1).
7. Female subjects and female partners of male subjects who plan to become pregnant during Treatment Period or within 90 days following the last dose of LUM/IVA.
8. Sexually active subjects of reproductive potential who are not willing to follow the contraception requirements outlined in Section 11.5.7.1.
9. History of solid organ or hematological transplantation.
10. Ongoing or prior participation in an investigational drug study (including studies investigating LUM and/or IVA) within 30 days of screening
  - A washout period of 5 terminal half-lives of the previous investigational LUM/IVA or 30 days, whichever is longer
  - The duration of the elapsed time may be longer if required by local regulations.
11. Current use of commercial LUM/IVA combination therapy.

12. Subject, or close relative of the subject, is the investigator or a subinvestigator, research assistant, pharmacist, study coordinator, or other staff directly involved with the conduct of the study at that site.

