**Table 11-1 Safety Laboratory Test Panels**

Serum Chemistry	Hematology
Total Bilirubin, direct bilirubin	Hemoglobin
Alkaline phosphatase	Erythrocytes:
Aspartate aminotransferase	Mean corpuscular hemoglobin
Alanine aminotransferase	Mean corpuscular hemoglobin concentration
Gamma-glutamyl transferase	Mean corpuscular volume
	Platelets
	Reticulocytes (absolute)
	Leukocytes
	Differential (absolute and percent):
	Eosinophils
	Basophils
	Neutrophils
	Lymphocytes
	Monocytes

**Pregnancy ( $\beta$ -human chorionic gonadotropin) Tests for Females of Childbearing Potential:** Serum (Screening only) and urine pregnancy tests will be performed at the site as specified in [Table 3-1](#) and [Table 3-2](#). The serum and urine pregnancy tests will be analyzed at the central laboratory. The urine pregnancy test on Day 1 must be negative before the first dose of LUM/IVA. Additional urine pregnancy tests may be required according to local regulations and/or requirements

If a urine pregnancy test is positive, all LUM/IVA dosing will stop and the pregnancy will be confirmed with a serum  $\beta$ -human chorionic gonadotropin test. If confirmed, the pregnancy will be reported and the subject will be permanently withdrawn from LUM/IVA (Section 11.5.7.2). If a pregnancy test is positive, the procedures outlined in Section 11.5.7.2 will be followed.

**Follicle-stimulating hormone (FSH) (Screening Period only):** Blood sample for FSH will be measured for any suspected postmenopausal female with at least 12 months of continuous

spontaneous amenorrhea. Serum FSH levels must be within the postmenopausal reference range of the performing laboratory to be considered postmenopausal.

CFTR genotype (Screening Period only): *CFTR* genotyping will be performed to confirm the subject is homozygous for the *F508del-CFTR* mutation as documented in the subject's medical record. The results of the genotype must be obtained and reviewed during the Screening Period. CF genotyping can be waived if the subject has a documented genotype result from a previous Vertex study with a Screening Visit date of 01 June 2010 or later. Specific instructions will be provided in the Laboratory Manual.

Additional Evaluations: Additional clinical laboratory evaluations will be performed at other times if judged to be clinically appropriate.

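### Section 11.5.7.1 sets the postmenopausal FSH cut-off at 40 mIU/L (0.04 mIU/mL), which conflicts with the laboratory-range rule in Section 11.5.2 and Table 3-1

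*Protocol*

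**What the plan says.** The protocol states postmenopausal status in three places.

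- **Section 11.5.7.1, Definition of Childbearing Potential.** A woman who has had her first period counts as being of childbearing potential, even after tubal ligation, unless she has had a documented hysterectomy or removal of both ovaries, or is postmenopausal, "defined as at least 12 months of continuous spontaneous amenorrhea with serum FSH levels $\geq 40$ mIU/L". The definition runs from screening through the Safety Follow-up Visit.
- **Section 11.5.2, FSH text after Table 11-1.** "Serum FSH levels must be within the postmenopausal reference range of the performing laboratory to be considered postmenopausal".
- **Table 3-1, footnote f (repeated in SAP Table 11-1).** Women past puberty count as being of childbearing potential. Besides a one-year postmenopausal period, the footnote's exceptions turn on whether they "have documented FSH levels within the postmenopausal reference range of the performing laboratory, or are surgically sterile".

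The status is used in three main places. Exclusion 6 says that "females of childbearing potential must have a negative pregnancy test at screening and Day 1". Table 3-2 schedules urine tests for women of childbearing potential, and that row carries no footnote to either definition. Exclusion 8 refers sites to Section 11.5.7.1 for the contraception requirements.

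**The concern.** One safety status has two FSH rules. Section 11.5.7.1 uses a fixed number; the other two places use the laboratory's range. Both are worded categorically, and no text ranks them or reconciles them.

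The fixed number also looks wrong. At 40 mIU/L it is so low that the FSH test would confirm little beyond the amenorrhea history.

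What is at stake is pregnancy testing during treatment. A site that applies Section 11.5.7.1 could record a woman as not of childbearing potential although Section 11.5.2 would not allow it. Her urine tests would then not be done. The Day 1 test must be negative before the first dose, and a later positive test stops dosing. A test that is not done can do neither.

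**Working it through.** **Inputs.** The fixed cut-off is in Section 11.5.7.1. The range rule is in Section 11.5.2 and Table 3-1 footnote f. The test schedule is in Tables 3-1 and 3-2. The documents give no laboratory FSH range, so a lower limit of 15 to 50 mIU/mL is assumed below, for illustration only.

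**Unit.** 40 mIU/L ÷ 1000 mL/L = 0.04 mIU/mL.

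**Where the rules disagree.** Take a woman with at least 12 months of spontaneous amenorrhea, and let L be the laboratory's lower limit for postmenopausal FSH. Section 11.5.7.1 calls her postmenopausal if FSH ≥ cut-off; the range rule does so if FSH ≥ L (a value above the range's upper end is ignored here).

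| Assumed L (mIU/mL) | Cut-off as printed, 0.04 mIU/mL: postmenopausal under 11.5.7.1 only | Cut-off if 40 mIU/mL was meant |
|---|---|---|
| 15 | 0.04 to 14.99 | 15 to 39.99: postmenopausal under range rule only |
| 25 | 0.04 to 24.99 | 25 to 39.99: postmenopausal under range rule only |
| 40 | 0.04 to 39.99 | none |
| 50 | 0.04 to 49.99 | 40 to 49.99: postmenopausal under 11.5.7.1 only |

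With the printed unit, every disagreement goes one way: Section 11.5.7.1 releases a woman whom the range rule keeps in testing. Correcting the unit alone does not remove the conflict unless L happens to be 40.

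**Tests that depend on the rule.** A woman of childbearing potential has 1 serum test at screening and 6 urine tests (Day 1, Weeks 12, 24, 36 and 48, and follow-up): 1 + 6 = 7. Footnote f, with the range rule, is attached to the serum row, so that test is not counted. That leaves 6 urine tests, or 6 − 1 = 5 if follow-up is not required, because "Subjects who begin commercial LUM/IVA before this visit do not have to complete the Safety Follow-up Visit".

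**Contraception.** The waiver list in Section 11.5.7.1 covers true abstinence and male infertility. It has no entry for postmenopausal women, so no waiver follows from the cut-off.

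**Analysis.** Outside its schedule tables, the SAP uses the status only to list abnormal pregnancy tests (SAP 8.4.2).

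**Tubal ligation, a secondary difference.** Footnote f exempts the surgically sterile without defining the term, and it can be read to include tubal ligation. Section 11.5.7.1 keeps those women in childbearing potential. At most the 1 screening serum test depends on this.

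**The case against.** The strongest reply is that Section 11.5.2 already settles the matter. It makes an FSH value in range a necessary condition for postmenopausal status, and it sits with the instructions for the serum and urine pregnancy tests. Any plausible in-range value also exceeds 40 mIU/L, so a site that applies both texts ends up with the range rule. Tests are lost only if a site prefers Section 11.5.7.1 to a mandatory statement elsewhere. This limits the practical effect. It does not remove the contradiction, because Section 11.5.7.1 is equally categorical, is the only text headed as the definition of childbearing potential, and covers the whole period of the urine tests.

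A second reply is that sites may read the cut-off as mIU/mL. The rule could then be stricter than the laboratory range and keep some women in testing unnecessarily. That is fair: the scope given here applies to the text as printed. The two rules would still differ.

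Third, few such women are expected. FSH is measured only in suspected postmenopausal subjects, Section 5.1 puts predicted median survival in CF at about 40 years, and the SAP records that the study was terminated early. All of this stands and supports a low rating. The difference in duration wording (12 months of amenorrhea against one year postmenopausal) also carries little weight, because footnote g of Table 3-1 uses the amenorrhea wording too.

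Lastly, exclusion 8 covers only subjects of reproductive potential, so one could argue that a woman classed as postmenopausal falls outside the contraception requirement as well. The text does not settle this, and no such effect is counted here.

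**Conclusion.** The point holds as a minor unit and consistency error in a safety definition. Read literally, it affects only women with at least 12 months of spontaneous amenorrhea and FSH of at least 40 mIU/L but outside the laboratory's postmenopausal range. For each such woman, 6 urine tests (or 5) turn on which section the site follows. The number of such women is not given and may be zero.

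The conflict between a fixed cut-off and a laboratory range rests on the documents alone. That the unit is a slip for mIU/mL is an assumption, and so are the lower limits in the table. No calculation in the plan is wrong, and the adherence endpoints, sample size and analyses are unaffected.

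**What to change.** In Section 11.5.7.1, replace the fixed FSH value with the requirement already in Section 11.5.2, that FSH lie in the performing laboratory's postmenopausal range. Add a footnote to the urine-test row of Table 3-2 pointing to that single definition. In footnote f of Table 3-1 and of SAP Table 11-1, replace the undefined term for surgical sterility with the procedures that Section 11.5.7.1 names: documented hysterectomy, or bilateral oophorectomy or salpingo-oophorectomy.

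This costs a few words in four places. Section 11.5.2 allows only central laboratory results for study conduct, so one FSH range should serve all sites. As the study has been terminated, the remaining step is to compare any FSH-based postmenopausal classification with that range, and to correct the wording before it is reused.

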**Contraception for the couple is waived for the following:**

- True abstinence for the subject, when this is in line with the preferred and usual lifestyle of the subject. Periodic abstinence (e.g., calendar, ovulation, symptothermal, postovulation methods) and withdrawal are not acceptable methods of contraception.
- If the male is infertile (e.g., bilateral orchectomy). Infertility may be documented through examination of a semen specimen or by demonstration of the absence of the vas deferens by ultrasound before the first dose of LUM/IVA.

**Acceptable Contraceptive Methods**

Acceptable contraceptive methods for **male subjects** or **male partners** of female subjects include the following:

- Vasectomy 6 months or more previously, with a negative postvasectomy semen analysis for sperm
- Condom with spermicide (either as a single product if commercially available and/or allowed according to local regulations; otherwise, condom and spermicide as separate products). Local regulations may require use of an additional acceptable method of contraception.

Acceptable contraceptive methods for **female subjects** include the following:

- Bilateral tubal ligation performed at least 6 months previously
- Continuous use of an intrauterine device (nonhormone-releasing) for at least 90 days
- Barrier contraception (such as diaphragm, cervical cap, or female condom) with spermicide. Local regulations may require use of an additional acceptable method of contraception.
- Note: Hormonal contraceptives, including oral, injectable, transdermal, and implantable, will not be considered as an effective method; however, female subjects are not required to discontinue hormonal contraceptives.

Acceptable contraceptive methods for **female partners** of male subjects:

- Bilateral tubal ligation performed at least 6 months previously
- Continuous use of an intrauterine device for at least 90 days (nonhormone-releasing and hormone-releasing intrauterine devices are permitted)
- Barrier contraception (such as diaphragm, cervical cap, or female condom) with spermicide. Local regulations may require use of an additional acceptable method of contraception.
- Hormonal contraceptives, if successfully used for at least 60 days

**Additional notes:**

- Female condom cannot be used with male condom (as a double method of contraception) due to risk of tearing.

- Male and female subjects who are not sexually active at the time of screening must agree to follow the contraceptive requirements of this study if they become sexually active with a partner of the opposite sex.
- If applicable, additional contraception requirements may need to be followed according to local regulations and/or requirements.
- Male subjects must not donate sperm after the first dose of LUM/IVA, throughout the study, and for 90 days following the last dose of LUM/IVA.
- Female subjects and female partners of male subjects should not plan to become pregnant during the study through 90 days following the last dose of LUM/IVA.
- Female subjects should not nurse a child from the start of LUM/IVA dosing through 90 days following the last dose of LUM/IVA.

Unique situations that may not fall within the above specifications may be discussed with the Vertex medical monitor or authorized designee on an individual basis.

### 11.5.7.2 Pregnancy

Subjects will be counseled to inform the investigator of any pregnancy that occurs during study treatment and for 90 days after the last dose of LUM/IVA.

If a subject or the female partner of a male subject becomes pregnant while participating in the study, LUM/IVA will be permanently discontinued immediately. The investigator will notify the medical monitor and Vertex Global Patient Safety (GPS) within 24 hours of the site's knowledge of the subject's (or partner's) pregnancy using the Pregnancy Information Collection Form.

If confirmed to be on active drug, the subject or partner will be followed until the end of the pregnancy and the infant will be followed for 1 year after the birth, provided informed consent is obtained. A separate ICF will be provided to explain these follow-up activities. Pregnancy itself does not constitute an AE.

## **12 STATISTICAL AND ANALYTICAL PLANS**

This section presents a summary of the planned statistical analyses for this protocol. Statistical analysis details will be provided in the Statistical Analysis Plan (SAP).

[figure not shown]
The Vertex Biometrics department or a designated CRO will analyze the data derived from this study. SAS® Version 9.2 or later will be used to generate all statistical outputs (tables, figures, listings, and data sets).

### **12.1 Sample Size and Power**

A total of approximately 75 subjects will be enrolled and will be randomized at 2:1 ratio to 1 of 2 study arms: Study Arm A (approximately 50 subjects) and Study Arm B, (approximately 25 subjects).

The primary endpoint is the mean percentage adherence to LUM/IVA treatment over 48 weeks. Assuming a standard deviation (SD) of 8, a sample size of 50 in Study Arm A and 25 in Study Arm B will have 80% power to detect a difference of 5.6% between the means for the 2 study arms using a 2-sided, 2-sample *t*-test at the 0.05 significance level.

Data from studies VX09-809-102, VX12-809-103, and VX12-809-104 were used for this sample size calculation. Sample sizes based on a range of SDs [REDACTED].

